3.8 Center pooling strategy

Centers will be grouped in the geographic regions North America (country codes USA, CAN), Western Europe (country codes DEU, ESP) and Eastern Europe (country codes BGR, CZE, HUN, POL, RUS and UKR) for use as a covariate in statistical analyses and for sub-group analyses (see [Section 4.1](#) and [Section 8.4](#)). An additional region grouping of North America (country codes USA, CAN) and Europe (country codes BGR, CZE, DEU, ESP, HUN, POL, RUS and UKR) will be derived in the datasets for possible use in future integration.

3.9 Coding dictionaries

Medical history and AEs will be coded using the Medical Dictionary for Regulatory Activities (MedDRA) version 19.0. Medical history conditions and AEs will be classified by primary system organ class (SOC) and preferred term (PT). AEs will be classified by primary system organ class (SOC), high level term (HLT) and preferred term (PT).

Prior and concomitant medications will be coded using version MAR2021 of the World Health Organization Drug Dictionary and will be classified by Anatomical Therapeutic Chemical (ATC) Main Group, Pharmacological Subgroup, and PT.

Medical procedures will not be coded.

3.10 Changes to protocol-defined analyses

The following changes have been made to the protocol-defined analyses:

- Change from AS0009 EV for safety variables will no longer be presented, since the EV assessment is made after 36 or 48 weeks of bimekizumab treatment and there is unlikely to be any further important change.
- Change from AS0008 Baseline and AS0009 EV for laboratory variables will not be presented, due to a change in laboratory vendor between AS0008 and AS0009. Laboratory Baseline has been defined as the earliest value in AS0009 at or prior to AS0009 Week 12.
- Summaries of ASAS40, ASAS20 and ASAS5/6 response at each post-AS0008 Baseline visit have been added for subjects who were responders at AS0008 Week 12. These summaries include all post-AS0008 Baseline visits through to AS0009 Week 208, for subjects in the FAS for AS0009, and will be used to assess maintenance of response.
- The protocol describes the FAS as consisting of all enrolled subjects who receive at least 1 dose of IMP and have a valid measurement for at least 1 efficacy variable at AS0009 study entry. This has been updated to include all subjects in the ES who received at least one dose of study medication in AS0009 and have a valid measurement for at least one efficacy variable at a scheduled visit (excluding SFU visits) after AS0009 EV. This was updated in order to identify subjects who have had assessments during AS0009 and which contribute to any of the efficacy analyses.
- Summaries by randomized treatment in AS0008 will not be produced, as subjects will have been on a constant dose of bimekizumab 160mg or 320mg for at least 36 weeks prior to AS0009 entry. Maintenance of response displays will be split by treatment sequence across AS0008 and AS0009. Safety displays using AS0008 information will incorporate exposure in AS0008.
- The protocol defines subgroups based on ‘Concomitant non-steroidal anti-inflammatory drug (NSAID) status at AS0009 entry. This has been updated to ‘Concomitant NSAID status at start of AS0008’.
- The protocol stated that all safety analysis would be performed for both Sub-populations; instead only key safety analyses will be repeated by Sub-population as identified in [Section 10](#). These analyses will be performed only in the event that the number of subjects receiving rescue medication is $\geq 10\%$ of the total number of subjects in the SS.

3.10.1 Changes related to COVID-19

The impact of the COVID-19 pandemic on study procedures/conduct and on the primary safety endpoints (TEAEs, serious TEAEs and study withdrawal due to TEAEs) will be investigated and

additional outputs provided as appropriate. These analyses were not planned as part of the protocol as the pandemic was not ongoing at the time of protocol finalization.

The additional analyses are described in the following sections of the SAP:

- Subject disposition, including details of impacted visits and effects on collection and reporting of efficacy data ([Section 5.1.1](#))
- Adverse events ([Section 10.2.4](#))

4 STATISTICAL/ANALYTICAL ISSUES

4.1 Adjustments for covariates

All multiple imputation (MI) models (see [Section 4.2.1](#)) will include the following covariates:

- Geographic region at AS0008 Baseline (North America, Western Europe, Eastern Europe), as defined in [Section 3.8](#).
- Previous (past) tumor necrosis factor (TNF) inhibitor agent exposure in AS0008. The value in the AS0008 database for past anti-TNF therapy (as collected on the eCRF) will be used for AS0009, without additional derivation.

Missing efficacy data will be handled as described in [Section 4.2.1](#). No imputation will be made for missing safety or background data, except as described in [Section 4.2.2](#) and [Section 4.2.3](#).

4.2 Handling of dropouts or missing data

4.2.1 Handling of missing data for efficacy analysis

Calculation of derived efficacy variables in the presence of missing data is described in individual sub-sections of [Section 8.1](#). All derived efficacy variables will be calculated using observed data, and any resulting missing data will be handled as described in this section. All non-responder imputation (NRI) and multiple imputation (MI) as described below will be performed only for subjects in the FAS for AS0009.

For assessments missing during AS0008 which are used in AS0009 for reporting maintenance of response, the imputed value (based on NRI) from the AS0008 database will be used.

For all visits in AS0009 (including AS0009 EV), missing values or values which cannot be constructed due to missing components for binary secondary/other efficacy variables (ASAS40, ASAS20, ASAS5/6) will be imputed using NRI. For each visit, subjects with missing data or who have dropped out of the study will be counted as non-responders. This includes any subjects with missing baseline values.

For missing continuous secondary/other efficacy variables an MI approach will be used. This will be performed for the following variables/endpoints:

- ASAS components:
 - Total Spinal Pain, Question 1 from TNSP
 - Inflammation, derived as the mean of Question 5 and 6 from the BASDAI
- ASDAS-CRP components:

- Total Back Pain, Question 2 from the BASDAI
- Duration of Morning Stiffness, Question 6 from the BASDAI
- PGADA (this is already included below as this is required as a standalone endpoint)
- Peripheral Pain/Swelling, Question 3 from the BASDAI
- CRP

ASDAS-CRP and ASDAS-ID will be determined after MI of the individual components of the ASDAS-CRP (ie, MI will not be applied to the overall ASDAS-CRP score). Note that for CRP the rules for handling measurements that are below the limit of quantification (BLQ) should be followed as per [Section 8.1.2](#). Thus, if any imputed values are <2mg/L these will be replaced with a constant value of 2mg/L for subsequent derivation of ASDAS-CRP. For the ASDAS-ID, the number of subjects within each disease activity category will be derived for each imputation and the mean number of subjects within each category across imputations will be presented.

- BASDAI
- BASFI
- BASMI
- MASES
 - For MASES the MI model will be restricted to subjects with a MASES score > 0 at AS0008 Baseline. Subjects with a MASES score of zero at AS0008 Baseline will be excluded prior to performing the procedure outlined below.
- PGADA
- TNSP
- SF-36
 - For SF-36 this will be performed for the Physical Component Summary score (PCS) and Mental Component Summary score (MCS) and for each of the 8 domain scores (Physical Functioning, Role Physical, General Health, Bodily Pain, Vitality, Social Functioning, Role Emotional and Mental Health).
- ASQoL
- HADS-A and HADS-D
 - Incidence of normal HADS-A and HADS-D scores (defined as having HADS-D<8 and HADS-A<8 at the same visit) will be derived at each visit using the values for HADS-A and HADS-D obtained after MI
- CRP
 - Note that for CRP as a standalone endpoint the rules for handling measurements that are below the limit of quantification should be followed as per [Section 8.1.12](#). Thus, if any

imputed values are <0.16mg/L these will be replaced with 0.08mg/L prior to any subsequent reporting.

The missing absolute value (not the change from baseline) will be replaced by one of a set of plausible values, where each value is a Bayesian draw from the conditional distribution of the missing data given the observed data. The basic assumption in MI is that the underlying missing data mechanism is ignorable, e.g. the missing data are missing at random.

All MI procedures will be performed using data from both AS0008 and AS0009 such that missing data across both studies will be imputed. Any previous MI or last observation carried forward (LOCF) (or other e.g., next observation carried backward) imputation performed in AS0008 will not be considered for AS0009 such that the procedure will use OC data only across both studies.

As the AS0008 Week 48 time point is synonymous with the AS0009 EV time point, this will be incorporated once only into the model.

The SAS® PROC MI procedure will be used for the imputation.

The MI consists of 3 steps:

- The missing data are imputed m times to create m complete datasets.
- The m datasets are summarized.
- The results of the m summaries are combined into a single result.

The MI method will be applied as follows:

Step 1

- Create a data set, sorted by treatment group at completion of AS0008, of subjects with observed values and missing values needing imputation. Missing values will be separated into non-monotone (ie, intermittent missing values between completed assessments) and monotone (ie, missing values after the subject dropped out). The procedure will sequentially estimate an imputation model for the efficacy variable at each post-AS0008 Baseline visit where efficacy variables are collected, with AS0008 Baseline, geographic region, and past TNF inhibitor exposure (as collected on the eCRF in AS0008 for past anti-TNF exposure) as covariates, separately for each treatment group at the completion of AS0008.
- Intermittent missing data will be imputed by draws from the imputation model using the Markov-Chain Monte Carlo (MCMC) method with multiple chains and monotone imputing. A total number of imputations will be 100. The seed used for these imputations will be 2017.

Note: All MI procedures described in this SAP will use the same seed.

- The post-AS0008 Baseline values will be specified in chronological order in the imputation model so that the SAS® PROC MI imputes variables from left to right. In case an AS0008 Baseline raw value is missing, the study participant will be excluded. The imputation model based on the MCMC method will only allow multivariate normal continuous variables as predictors. Therefore, past TNF inhibitor exposure and geographic region will be re-coded as indicator variables. For past TNF inhibitor exposure, this will be 0 for no past exposure and 1 for past TNF exposure. For region, there will be 2 indicator variables, the first of which will

be 1 for subjects from Western Europe and 0 for all other subjects and the second of which will be 1 for subjects from Eastern Europe and 0 for all other subjects. The order of the covariates in the model will be as follows: region indicator variables (Western Europe =1, Other =0; Eastern Europe=1, Other=0), past TNF inhibitor exposure (Yes=1, No=0), Baseline and then the visit variables.

- Once the intermittent missing data are imputed, the monotone missing data will be imputed including covariates as defined above, based on the datasets created by the intermittent missing data MI. Since this dataset already has 100 imputed values at each visit, only 1 imputation will be performed.

Step 2

The dataset with the imputed results for each treatment arm will be combined into one complete dataset including each of the 100 imputations. If any imputed value is less than the lower limit of the allowable range for that parameter (as shown in [Table 4-1](#)), it will be changed to the lower limit of the range, and similarly for values higher than the allowable range. This dataset will be used to calculate the change from AS0008 Baseline variable when appropriate.

Table 4-1: Allowable ranges for continuous efficacy variables

Variable	Minimum	Maximum
BASDAI	0	10
BASFI	0	10
BASMI	0	10
MASES	0	13
PGADA	0	10
TNSP	0	10
SF-36 MCS ^a	-3.33	80.09
SF-36 PCS	5.02	79.78
SF-36 Bodily Pain	21.68	62
SF-36 General Health	18.95	66.5
SF-36 Mental Health	11.63	63.95
SF-36 Physical Functioning	19.26	57.54
SF-36 Role Emotional	14.39	56.17
SF-36 Role Physical	21.23	57.16
SF-36 Social Functioning	17.23	57.34
SF-36 Vitality	22.89	70.42
ASQoL	0	18

Table 4-1: Allowable ranges for continuous efficacy variables

HADS-A	0	21
HADS-D	0	21
ASAS component score (Total Spinal Pain [Question 1 from TNSP])	0	10
ASAS component score (Morning stiffness [the mean of BASDAI Questions 5 and 6])	0	10
ASDAS-CRP component score (Total Back Pain [Question 2 from the BASDAI])	0	10
ASDAS-CRP component score (Duration of Morning Stiffness [Question 6 from the BASDAI])	0	10
ASDAS-CRP (Peripheral Pain/Swelling [Question 3 from the BASDAI])	0	10
ASDAS-CRP component score (CRP ^b)	2	NA
CRP ^c	0.08	NA

ASAS=Assessment in SpondyloArthritis International Society; ASDAS-CRP=Ankylosing Spondylitis Disease Activity Score-C-reactive protein; ASQoL=Ankylosing Spondylitis Quality of Life; BASDAI=Bath Ankylosing Spondylitis Disease Activity Index; BASFI=Bath Ankylosing Spondylitis Functional Index; BASMI=Bath Ankylosing Spondylitis Metrology Index; CRP=high sensitivity C-reactive protein; HADS-A=Hospital Anxiety and Depression Scale – Anxiety; HADS-D=Hospital Anxiety and Depression Scale – Depression; MASES=Maastricht Ankylosing Spondylitis Enthesitis Index; PGADA=Patient’s Global Assessment of Disease Activity; SF-36 MCS=Short Form 36-Item – Mental Component Summary; SF-36 PCS=Short Form 36-Item – Physical Component Summary; TNSP=Total Nocturnal and Spinal Pain.

^a SF-36 ranges are used for imputation purposes only. Any observed values outside the ranges based on norm-based scores will be reported as calculated in all tables and listings.

^b For the purposes of the MI any numerical CRP values obtained in AS0009 that were <0.16mg/L will be substituted with half the lower limit of quantification (LLOQ) from AS0008 (ie, 0.08mg/L) prior to performing the MI. Subsequently any observed or imputed values of <2mg/L will be replaced by the value of 2mg/L for the purposes of deriving the ASDAS-CRP. Any CRP values of >=500mg/L will be set to missing prior to performing the MI procedure.

^c For the purposes of the MI any numerical CRP values obtained in AS0009 that were <0.16mg/L will be substituted with half the LLOQ from AS0008 (ie, 0.08mg/L) prior to performing the MI. Subsequently any imputed values of <0.16mg/L will be replaced by the value of 0.08mg/L for the purpose of summaries based on imputed data. Listings will display the original result. CRP values of >=500mg/L will be set to missing prior to performing the MI procedure; the subsequently imputed CRP value will be included in the summary tables.

Step 3 (Excluding CRP)

The 100 imputed datasets will be combined, and simple means and standard errors will be calculated using Rubin’s rules (via SAS® PROC MIANALYZE). For calculation of other

descriptive statistics (median, Q1, Q3, minimum and maximum), Rubin's rules do not apply. Multiple imputation estimates will be computed by calculating arithmetic means of the estimates from the multiple repetitions of the imputation algorithm. Thus, for median, Q1, Q3, minimum and maximum the following approach will apply:

- The data will be summarized by treatment, visit and imputation and the summary statistics will be computed.
- Results will be summarized by taking the mean value of each summary statistic at each visit across all imputations.

The number of decimal places will remain the same as the original for display purposes (ie, if the mean was presented to 1 decimal place, the mean of the means will also be presented to 1 decimal place).

Step 3 (CRP only)

The CRP data will be presented using the geometric mean, 95% confidence interval (CI) for the geometric mean, median, Q1, Q3, minimum and maximum. The change from Baseline will be expressed as the ratio to Baseline in the summaries. The following approach will be applied:

- Following the MI procedure the ratio to Baseline will be calculated for any of the imputed values
- The natural logarithm of the absolute values and of the ratios to Baseline will be calculated
- The logged values will be summarized by treatment, visit and imputation
- The datasets will be combined using PROC MIANALYZE in order to get the mean and 95% CI estimates from the absolute values and ratios to Baseline (based on logged data) across imputations
- The estimates of the mean and 95% CI will be back-transformed to obtain the geometric mean and 95% CI on the original scale
- For the median, Q1, Q3, minimum and maximum the procedure outlined above for the other endpoints will be followed

As a sensitivity analysis, certain efficacy variables will be summarized based on observed data (see [Section 8](#)).

As a further sensitivity analysis for ASAS40 and ASAS20 responses, the response variables will be derived following MI of the individual components. The ASAS responses will then be derived for each subject and each imputation (where each imputation is performed across all individual components) and the number and percentage of subjects with each ASAS response in each imputation will be calculated. The mean value (across imputations) for the percentage of subjects with each ASAS response will be reported. Further details regarding data handling for the derivation of the ASAS response are provided in [Section 8.1.1.1](#) and will be implemented accordingly.

A similar approach will be followed for the calculation and summary of the number and percentage of subjects with normal HADS scores (defined as having HADS-D<8 and HADS-A<8 at the same visit) based on the HADS-D and HADS-A values after MI.

Primary and sensitivity analyses are summarized in **Table 4–2**. All summaries presenting data following MI will include only visits from AS0009 EV onwards (although the MI procedure will incorporate data from both AS0008 and AS0009).

Table 4–2: Missing data handling

Variable	Type	Missing data handling approach		
		NRI	MI/MCMC (monotone regression)	OC
ASAS40, 20	Responder	P	S ^a	S
ASAS component score (Total Spinal Pain [Question 1 from TNSP])	Continuous		P	
ASAS component score (Morning stiffness [the mean of BASDAI Questions 5 and 6])	Continuous		P	
ASAS5/6	Responder	P		S
BASDAI	Continuous		P	S
ASAS-PR	Responder	P		S
ASDAS-CRP	Continuous		P ^b	
ASDAS-CRP component score (Total Back Pain [Question 2 from the BASDAI])	Continuous		P	
ASDAS-CRP component score (Duration of Morning Stiffness [Question 6 from the BASDAI])	Continuous		P	
ASDAS-CRP (Peripheral Pain/Swelling [Question 3 from the BASDAI])	Continuous		P	
ASDAS-CRP (CRP ^c)	Continuous		P	
ASDAS-ID (including Moderate, High and Very High Disease Activity Categories)	Responder		P ^a	
BASFI	Continuous		P	
BASMI	Continuous		P	
MASES	Continuous		P	
PGADA	Continuous		P	
TNSP	Continuous		P	
SF-36 PCS, MCS and domain scores	Continuous		P	

Table 4–2: Missing data handling

ASQoL	Continuous		P	
HADS-A, HADS-D	Continuous		P	
Incidence of normal depression/anxiety status (using HADS)	Responder		P ^a	
CRP ^d	Continuous		P	

ASAS=Assessment in SpondyloArthritis International Society; ASAS-PR= Assessment in SpondyloArthritis International Society Partial Remission; ASDAS-CRP=Ankylosing Spondylitis Disease Activity Score-C-reactive protein; ASDAS-ID=Ankylosing Spondylitis Disease Activity Score-Inactive Disease; ASQoL=Ankylosing Spondylitis Quality of Life; BASDAI=Bath Ankylosing Spondylitis Disease Activity Index; BASFI=Bath Ankylosing Spondylitis Functional Index; BASMI= Bath Ankylosing Spondylitis Metrology Index; CRP=high sensitivity C-reactive protein; HADS-A=Hospital Anxiety and Depression Scale – Anxiety; HADS-D=Hospital Anxiety and Depression Scale – Depression; MASES=Maastricht Ankylosing Spondylitis Enthesitis Index; P=primary method; PGADA=Patient’s Global Assessment of Disease Activity; S=sensitivity method; SF-36 MCS=Short Form 36-Item – Mental Component Summary; SF-36 PCS=Short Form 36-Item – Physical Component Summary; TNSP=Total Nocturnal and Spinal Pain.

^a Imputation method is applied on continuous data, and responder variable is derived from the continuous data based on complete dataset.

^b Imputation for ASDAS-CRP overall score is based on the MI of the individual components of the ASDAS-CRP with subsequent recalculation of the overall ASDAS-CRP based on each imputation in turn; for each subject the mean of the ASDAS-CRP scores will be used in the summaries. Direct MI of the ASDAS-CRP overall score is not performed.

^c Refers to imputation of CRP for the purposes of calculating the ASDAS-CRP.

^d Refers to imputation of CRP for the summaries of CRP as a standalone endpoint.

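### ASDAS categories and normal HADS status are counted from components imputed one at a time under one shared seed, so the residual correlation between those components is modelled nowhere

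*SAP*

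**What the plan says.** SAP 4.2.1, Step 1, describes one model per variable: "The procedure will sequentially estimate an imputation model for the efficacy variable at each post-AS0008 Baseline visit where efficacy variables are collected". It is fitted separately by treatment group at completion of AS0008. After the region indicators, the predictor order is "past TNF inhibitor exposure (Yes=1, No=0), Baseline and then the visit variables". No other component appears. On the random draws it says "A total number of imputations will be 100. The seed used for these imputations will be 2017", and adds "All MI procedures described in this SAP will use the same seed".

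Two other places confirm component-by-component imputation. SAP 8.1.1.1 drops an ASAS component without a Baseline from the MI and keeps the others. The variable list in 4.2.1 takes PGADA from its standalone entry instead of imputing it with the other ASDAS items.

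The composites are built afterwards:
- **ASDAS:** "ASDAS-CRP and ASDAS-ID will be determined after MI of the individual components of the ASDAS-CRP". Category counts are taken in each imputation and averaged.
- **Normal HADS** (both scores below 8 at one visit): it "will be derived at each visit using the values for HADS-A and HADS-D obtained after MI", with percentages averaged over imputations.
- **ASAS40/20 sensitivity analysis:** "The ASAS responses will then be derived for each subject and each imputation (where each imputation is performed across all individual components". SAP section 8 instead derives the response from component scores averaged over imputations.

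Table 4-2 gives MI as the only method for ASDAS-CRP, its categories and normal HADS. For ASAS40/20 the primary method is NRI, with MI and observed-case analyses as sensitivity.

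**The concern.** An ASDAS sum below 1.3, two HADS scores both below 8, and three of four ASAS domains improved are joint events. When they are counted inside each imputed data set, the result depends on how the imputed components vary together. Separate models estimate each component's residual spread but not the correlation between residuals. With one seed for every run, that correlation is set by whether the random streams line up: close to 1 if the same subjects and visits are missing, lower if not.

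The patterns can differ. SAP 5.1.1 says CRP is missing at remote visits, where questionnaires may still be collected. CRP is then imputed without the subject's own questionnaire scores from the same visit.

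At stake are the reported ASDAS category and normal-HADS percentages, which have no NRI or observed-case analysis beside them. Treatment lasts up to 204 weeks, so dropout can accumulate.

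**Working it through.** **Plan figure.** There is none to reproduce. SAP 2.4 gives no formal sample size, and no dropout rate or MI result is stated.

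**Mechanism.** Write an imputed component as its fitted value from its own history plus s·z, where z is the random draw. The fitted values carry some between-component correlation from the data. The correlation ρ between the z of different components is not in any model. For the ASDAS sum, with weights w from SAP 8.1.2 and a = w·s, the residual SD for one imputed subject at a common ρ is

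SD = √[Σa² + ρ((Σa)² − Σa²)].

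Assume s = 1.5 for the four patient-reported items and 0.6 for ln(CRP+1). Then a = 0.1815, 0.0870, 0.1650, 0.1095 and 0.3474, so Σa = 0.890 and Σa² = 0.200. The SD is √0.200 = 0.45 at ρ = 0 and 0.89 at ρ = 1. No table reports this quantity. It shows only why a count below 1.3 depends on ρ.

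**Study-level simulation.** Design: 250 subjects, Baseline plus 6 visits, monotone dropout, Bayesian monotone regression, 40 replicates, 20 imputations (the SAP uses 100). Assumed, because the documents give no values: dropout of 10-30%, means and SDs, and a same-visit correlation between components of about 0.6 or about 0.37. Simplifications: ln(CRP+1) normal, no 2 mg/L floor, no intermittent gaps, numpy in place of SAS.

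Correlation of the imputation noise between two components:
- joint imputation: 0.51-0.54 (0.30-0.34 at the lower setting)
- separate models, same seed, matching patterns: 0.97-0.99
- separate models, shifted streams: about 0.3-0.5
- separate models, independent streams: about 0

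The total correlation of imputed values under independent streams was still 0.26-0.30 (true 0.6) or 0.08-0.11 (true 0.37), carried by each component's own history.

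Percentages, with shifts from joint imputation in brackets (computed before rounding where possible):

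| Dropout, correlation | Outcome | Full data | Joint | Same seed, matched | Independent |
|---|---|---|---|---|---|
| 10%, 0.6 | ASDAS-ID | 20.5 | 20.9 | 21.1 (+0.2) | 20.1 (-0.8) |
| 10%, 0.6 | Normal HADS | 74.1 | 73.9 | 74.2 (+0.3) | 73.7 (-0.2) |
| 30%, 0.6 | ASDAS-ID | 20.5 | 20.8 | 21.3 (+0.5) | 18.4 (-2.4) |
| 30%, 0.6 | Normal HADS | 74.1 | 73.6 | 74.5 (+1.0) | 72.8 (-0.8) |
| 30%, 0.37 | ASDAS-ID | 16.1 | 16.4 | 18.3 (+1.9) | 13.8 (-2.6) |
| 30%, 0.37 | Normal HADS | 71.9 | 70.9 | 72.7 (+1.8) | 70.5 (-0.4) |

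Against full data in the 30%, 0.37 setting, ASDAS-ID is off by +0.3 (joint), +2.1 (same seed) and -2.3 (independent), so joint imputation is clearly better. Normal HADS is off by -1.0, +0.8 and -1.4, so joint imputation does not beat the matched seed there.

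ASAS40 derived per imputation shifted by -0.8 to +2.8 points from joint imputation, and ASAS20 by +0.2 to +1.4.

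**What does not move.** At 30% dropout and correlation 0.6, mean ASDAS-CRP is 2.09 in all schemes. Table 4-2, footnote b, summarises each subject's ASDAS-CRP averaged over imputations. The SD of that score is 0.840 (joint), 0.833 (same seed) and 0.826 (independent), against 0.904 with full data. The averaging causes the shortfall; the seed has almost no effect on it.

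**Check of the fix.** A second simulation used 130 subjects per group, 20 visits and 30% assumed dropout, with same-visit components added in the monotone step only. ASDAS-ID bias fell from +1.2 to +1.7 points (same seed) or -1.4 to -1.8 (independent streams) to about +0.5 to +0.6, with lower root mean squared error. Normal HADS improved only against independent streams.

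**The case against.** The best defence is that separate imputation is a reasonable choice at this size. A joint MCMC for ASAS would hold 4 components × (Baseline + 27 visits) + 3 indicators = 4 × 28 + 3 = 115 variables, with roughly 140 subjects per group if the cap of 285 splits evenly (assumed). The affected percentages are other efficacy variables, summarised descriptively in a single-arm safety extension. The repeated draws are an assumption about SAS. With shifted streams, the noise correlation of 0.3-0.5 even falls near the jointly imputed values. SAP 8.5 adds that the pandemic began after all subjects had completed Week 48, so the remote-visit example does not touch missing CRP at the secondary time point.

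Most of this stands as a limit on size and remedy: the effect is modest, and a full joint MCMC is not the answer. It does not remove the point. The gap does not depend on the seed, since separate models with independent streams leave residual correlation at 0 and gave the largest ASDAS-ID shift. A near-correct value under shifted streams would be luck.

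A reader might go further and infer that the correlation between imputed components is wholly an artefact of the random stream. The SAP does not support that, because every model conditions on the component's own Baseline and visits across both studies. A reader might also infer that the ASAS40/20 results are compromised. Their primary NRI analysis and the observed-case analysis use no MI, and the averaged-component derivation in SAP section 8 would largely remove the noise.

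**Conclusion.** The point holds in a limited form. The residual correlation between imputed components is not modelled, and this can bias the ASDAS-ID and other ASDAS category percentages and, less clearly, normal HADS. Under assumed dropout of 10-30% the shift from joint imputation is about -2.6 to +1.9 points for ASDAS-ID and -0.8 to +1.8 for normal HADS; at 10% it is about 1 point or less. The ASAS40/20 MI sensitivity analysis is affected only if the per-imputation derivation in 4.2.1 governs over section 8, and only if its wording about all components pairs imputation numbers and does not mean a joint model. No joint model is described anywhere.

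It would be too strong to call these percentages wrong in a known direction, or to say that the seed distorts the reported ASDAS-CRP spread. The sign depends on how the streams align, and footnote b's averaging makes the reported SD almost insensitive to the seed. Mean ASDAS-CRP, BASDAI (imputed as a total score) and the NRI analyses are essentially unaffected.

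The sizes rest on assumed dropout, correlations and SDs. The near-1 figure also rests on PROC MI repeating its draws under one seed.

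**What to change.** In SAP 4.2.1, Step 1:

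1. Keep the per-variable MCMC step for intermittent gaps.
2. In the monotone regression step, impute the components of each composite in one run: the five ASDAS-CRP components, HADS-A with HADS-D, and the four ASAS domains. Go visit by visit in a fixed order. Add to the present predictors the same-visit values of components already observed or imputed.
3. Say what is done when a subject's components end at different visits, since the combined sequence is then not monotone. Also state which imputed PGADA and BASFI values feed their own tables.
4. Limit the seed note to one seed per joint run. Changing seeds alone is not enough, because it leaves the residual correlation at 0.
5. Reconcile 4.2.1 with section 8 on how the MI-based ASAS response is derived, and Table 4-2, footnote b, with the per-imputation pooling in Step 3.

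The cost is SAP wording, reprogramming and up to four extra predictors per regression. No new data are needed. One limit remains: an intermittent gap, such as CRP missing at a remote visit and measured again later, would still be filled from that variable's own series.
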